4.1. Subject Inclusion Criteria

Subjects enrolled into this study must meet the following inclusion criteria to be eligible.

1. Subjects with histologically- or cytologically-confirmed recurrent or metastatic HNSCC considered incurable by local therapies, and subjects with T4 or N3 disease who are ineligible for or refusing local therapies.
2. No prior systemic therapy in the recurrent or metastatic setting. Systemic therapy as part of multi-modal treatment for locally advanced disease is allowed.
3. Primary tumor locations of oropharynx, oral cavity, hypopharynx, larynx, paranasal sinus, or HNSCC of unknown primary origin. Participants may not have a primary tumor site of nasopharynx (any histology).
4. Able to provide tissue from a core or excisional biopsy (fine needle aspirate is not sufficient). A newly obtained biopsy (within 90 days before the start of study treatment) is preferred but an archival sample is acceptable.
5. CPS ≥ 1 for PD-L1 on immunohistochemistry (IHC) of tumor tissue.
6. Have results of tumor HPV p16 by IHC for oropharyngeal or for unknown primary cancer.
7. Measurable disease as defined by RECIST v1.1, and both of the following:
 - a. At least 1 lesion amenable to repeated IT injection.
 - b. Documented disease progression in any lesion that was previously radiated in order to serve as a target lesion.
8. Adequate organ function based on most recent laboratory values within 3 weeks before the first dose of study drug on Week 1 Day 1 (W1D1):
 - a. Bone marrow function:
 - neutrophil count $\geq 1,500/\text{mm}^3$
 - platelet count $\geq 100,000/\text{mm}^3$
 - hemoglobin concentration $\geq 9 \text{ g/dL}$
 - b. Liver function:
 - total bilirubin ≤ 1.5 times the upper limit of normal (ULN) with the following exception: subjects with Gilbert Disease serum bilirubin ≤ 3 times ULN
 - aspartate aminotransferase and alanine aminotransferase ≤ 3 times the ULN or ≤ 5 times the ULN for subjects with active liver metastases
 - c. Renal function: estimated (Cockcroft-Gault) or measured CrCl $\geq 30 \text{ mL/min}$
 - d. Coagulation
 - International normalized ratio (INR) or prothrombin time (PT) ≤ 1.5 times ULN unless subject is receiving anticoagulant therapy as long as PT or PTT is within therapeutic range of intended use of anticoagulants

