9.6.2. Clinical Laboratory Assessments

Safety central laboratory data will be summarized using descriptive statistics (mean, standard deviation, median, minimum, and maximum), and presented for each time point, including change from Baseline, for the Safety Analysis Set. Shift from Baseline tables will also be created. The categories in the shift tables will be WNL, Low, and High. WNL and Normal will be used when appropriate for urinalysis parameters. Clinically significant post-Baseline laboratory values will be reported as AEs. By-subject data listings of all central laboratory data will be generated and all values outside the normal range will be flagged as High or Low. Listings of all clinically significant post-Baseline laboratory values from central laboratory assessments will be presented in the data listings.

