Regeneron Pharmaceuticals Inc. / Protocol: CMP-001-007
IQVIA Biotech (Confidential) Project # SZA56629

- TEAEs leading to CMP-001 treatment discontinuation
- TEAEs leading to pembrolizumab treatment discontinuation
- TEAEs leading to study discontinuation by SOC and preferred term

Additionally, subgroup analysis for the overall summary of adverse events by schedule will also be performed. A by-subject AE data listing, including verbatim term, SOC, preferred term, severity, outcome, and relationship to treatment, will be provided. Listed terms will be ordered alphabetically within subject. Separate listings will be generated for deaths, SAEs and AEs leading to treatment and study discontinuation.

C. Deaths

All deaths that occur during the study or within the protocol-specified follow-up period after the last dose of the study drug will be reported.

Death information to be included in the summary table concerns the incidence of deaths, along with the primary cause of death for the Treated Analysis Set. All deaths including deaths that occur within 30 days after the last dose of the study treatment or the initiation of an alternative new anti-cancer therapy, whichever is earlier, will be tabulated and presented in a by-subject listing, involving the primary cause of death, duration of treatment and the number of days between the last dose date of the study drug and death. Additionally, subgroup analysis for deaths by schedule will also be performed.

D. Clinical Laboratory Results

Gradable laboratory values will be evaluated and assigned toxicity grades according to the NCI CTCAE v5.0. Clinically significant post-baseline laboratory values will be reported as AEs. When possible, a diagnosis should be recorded as an AE, rather than the symptoms or isolated laboratory abnormalities related to the diagnosis.

Safety central laboratory data, including hematology, coagulation, serum chemistry, autoimmune lab panel and thyroid function tests (see Table 3 below), will be summarized using descriptive statistics (mean, standard deviation, median, minimum, and maximum) and presented for each time point, including change from Baseline, for the Treated Analysis Set. Shift tables from Baseline to the Min and Max Post-Baseline, the categories in the shift tables will be WNL, Low, and High. Within normal limits and Normal will be used when appropriate for urinalysis parameters.

Regeneron Pharmaceuticals Inc. / Protocol: CMP-001-007

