 IQVIA Biotech (Confidential) Project # SZA56629

By-subject data listings of all central laboratory data will be generated and all values outside the normal range will be flagged as High or Low. Listings of all clinically significant post-Baseline laboratory values from local and central laboratory assessments will be presented in the data listings.

Table 3: Clinical Laboratory Assessments

Hematology	Serum Chemistry	Urinalysis	Other Laboratory Tests
Red blood cells (RBCs)	Alanine aminotransferase (ALT)	Blood	Coagulation:
White blood cells (WBCs)	Albumin	Glucose	PTT
Differential WBC count	Alkaline phosphatase (ALP)	Nitrites	PT
Hemoglobin	Amylase	pH	INR
Hematocrit	Aspartate aminotransferase (AST)	Protein	
Platelets	Bilirubin	Specific gravity	Thyroid Function Studies:
	Blood urea nitrogen	WBCs	Thyroid Stimulating Hormone, Free T3, Free T4
	Calcium	Microscopic battery:	
	Chloride	RBCs, WBCs, epithelial cells, casts (only if significant positive findings on urinalysis)	Autoimmune laboratory Panel:
	Creatinine		Anti-dsDNA
	Glucose		Antinuclear
	Lactate dehydrogenase (LDH)		Antibody
	Lipase		Antineutrophil cytoplasmic antibody
	Phosphorous		Rheumatoid factor
	Potassium		Antibodies to ribonucleoprotein (anti-RNP)
	Sodium		
	Total protein		Tests to be performed as clinically indicated:
			Human immunodeficiency virus
			Hepatitis B and C

Abbreviations: Anti-dsDNA = anti-double stranded DNA; RBC = red blood cell; T3 = triiodothyronine; T4 = thyroxine; WBC = white blood cell.

Note: Refer to the Study Laboratory Manual for additional information.

E. Vital Signs

Vital signs include measurement of blood pressure (systolic and diastolic blood pressure), respiratory rate, heart rate, and body temperature. Summaries of actual values and changes from baseline will be presented for each assessment time point, beginning with the first post-baseline assessment.

Moreover, each of these vital signs will be summarized in a descriptive manner for the following values that will be derived per unique subject:

Regeneron Pharmaceuticals Inc. / Protocol: CMP-001-007
IQVIA Biotech (Confidential) Project # SZA56629

- Baseline value
- Minimum post-baseline value and corresponding change from baseline
- Maximum post-baseline value and corresponding change from baseline
- Last post-baseline value and corresponding change from baseline

A by-subject data listing of all vital sign data will be generated.

F. Physical Examination

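### SAP IX.D grades laboratory values by CTCAE but plans no laboratory summary that uses the grades, so its WNL/Low/High shift tables cannot show how severe a worsening was

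*SAP*

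**What the plan says.** SAP IX.D opens with a commitment to grade: "Gradable laboratory values will be evaluated and assigned toxicity grades according to the NCI CTCAE v5.0". The laboratory outputs it then specifies are:

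- descriptive statistics, including minimum and maximum, at each time point, with change from baseline;
- "Shift tables from Baseline to the Min and Max Post-Baseline", in which "the categories in the shift tables will be WNL, Low, and High" (with WNL and Normal used for urinalysis where appropriate);
- by-subject listings of central laboratory data, in which "all values outside the normal range will be flagged as High or Low";
- a listing of clinically significant post-baseline values from local and central laboratories.

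None of these is specified by grade. Protocol 9.6.2 fixes the same shift categories: "The categories in the shift tables will be WNL, Low, and High".

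Protocol 4.1, inclusion criterion 8, allows abnormal values at entry. For transaminases the limit is "aspartate aminotransferase and alanine aminotransferase ≤ 3 times the ULN or ≤ 5 times the ULN for subjects with active liver metastases". Total bilirubin may be up to 1.5 x ULN, or 3 x ULN in Gilbert disease. SAP II.C reports that 24 subjects started treatment.

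**The concern.** A three-category shift table works when subjects start within normal limits and the question is whether they leave them. Here some subjects may start outside normal limits. For them, further worsening in the same direction cannot change the category. For subjects who start normal, the table records that a limit was crossed but not by how much.

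The SAP gives laboratory data no other summary of each subject's worst value. Vital signs (IX.E) and ECGs (IX.I) get per-subject minimum, maximum and last post-baseline values with change from baseline, and ECOG status (IX.J) gets a shift to the worst score. For laboratory data the shift table does that job alone.

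At stake is a plain safety statement: how many subjects reached each laboratory grade, and from what starting grade. The SAP plans to derive the grades that would answer this and then gives them no stated use in a table.

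**Working it through.** The plan states no figure to reproduce, and no sample size or error rate is involved. The check applies the SAP's categories to the protocol's own entry limits.

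**Inputs.** Entry limits come from Protocol 4.1, criterion 8. A value above 1 x ULN is classed High. The multipliers 2, 5 and 10, and the normal-entry values in the last row, are assumptions chosen for illustration.

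**Rule.** Worst value = baseline x multiplier. The shift cell is the category at baseline to the category at the post-baseline maximum.

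| Case | Baseline (x ULN) | Worst value (x ULN) | Cell |
|---|---|---|---|
| ALT/AST, no active liver metastases | 3 | 6, 15, 30 | High to High |
| ALT/AST, active liver metastases | 5 | 10, 25, 50 | High to High |
| Bilirubin | 1.5 | 3, 7.5, 15 | High to High |
| Bilirubin, Gilbert disease | 3 | 6, 15, 30 | High to High |
| Subject entering normal | 0.8 | 1.2 or 15 | WNL to High (both) |

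In the first four rows every degree of worsening falls in the cell that an unchanged value would occupy. In the last row a small and a very large excess cannot be told apart.

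**Do the per-visit statistics fill the gap?** Suppose one of 24 subjects goes from 3 to 15 x ULN, the other 23 do not change, and all 24 are assessed. The mean change is (15 - 3)/24 = 0.5 x ULN. The mean barely signals the event. The visit maximum would show the value of 15 x ULN, but not how many subjects reached a severe level.

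**Limits of the check.**

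- Masking applies only to worsening in the same direction as the baseline abnormality. A move to the opposite side would show as a shift.
- The documents give no CTCAE laboratory cut-points, so no grade is attached to these multiples.
- Hemoglobin and platelet entry limits are absolute values. Whether a subject at those limits is Low depends on laboratory reference ranges that the documents do not give. The ALT/AST and bilirubin examples are stated in multiples of ULN and do not have this problem.

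**The case against.** The strongest reply is that severity is reported elsewhere, and much of it stands.

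- **Endpoint.** The secondary safety endpoint is the CTCAE severity of adverse events, not the grade of laboratory values. SAP IX.B tabulates it in full: Grade 3 or higher TEAEs, TEAEs by maximum severity, and the same by relationship to each drug. A reader might infer that a stated endpoint goes unanalysed. It does not.
- **AE capture.** Protocol 8.1.1 counts a test abnormality as an AE if it alters care or is judged clinically significant, and counts a baseline abnormality that worsens. Protocol 7.1.13 has the Investigator assess every out-of-range central result for clinical significance. A reader might infer that severe worsening would go unrecorded. These rules make that unlikely for marked changes. Some dependence on judgement remains, and both Protocol 8.3 and SAP IX.D prefer a diagnosis to an isolated laboratory abnormality. The TEAE tables therefore do not count subjects by laboratory grade.
- **Other displays.** Per-visit minima and maxima and the by-subject listings would show extreme values, and listings for 24 subjects can be read through. But they are not a count.
- **Permissive wording.** SAP VI.K allows some continuous variables to be grouped into categories for frequency tables, and its general listing rule covers derived data, which could include grades. This permits a grade table but does not commit to one. IX.D, the specific section, names only WNL/Low/High.
- **Status of the study.** Enrolment stopped early and all analyses are descriptive and exploratory. No hypothesis test rests on this table. This limits the weight of the point, but clear description is then what the tables are for.

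**Conclusion.** The point holds as a limitation of the laboratory summary tables. The SAP assigns grades and specifies no laboratory summary that uses them, and the one worst-value table it plans cannot show same-direction worsening from an abnormal baseline or separate mild from severe shifts from a normal one. This follows from the categories and the entry limits alone, whichever multipliers are chosen.

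It does not hold as a claim that toxicity is hidden from the report as a whole: the AE tables, maxima, minima and listings may still show the same cases.

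Its size in this study cannot be stated. The documents do not say how many of the 24 subjects entered with abnormal values, and the number could be zero. One subject is 1/24 = 4.2% of the treated set, and a reader might take that as the incidence missed per case. It is only the weight of any single subject, not a measure of impact.

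This is a worthwhile, low-cost improvement to the safety displays. It corrects no bias and changes no inference.

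**What to change.** In SAP IX.D, for CTCAE-gradable parameters, add a shift table of baseline grade to worst post-baseline grade. Present it separately by direction where a parameter is graded both high and low, and include the number and percentage of subjects reaching Grade 3 or higher. Keep the WNL/Low/High tables for parameters that cannot be graded.

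The cost is a sentence or two in the SAP and a few extra tables to program. The grades are already to be derived, so no new data are needed, and sample size and error rates are unaffected.
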